8.2 Statistical Methods

There are no planned interim analyses for this minimum-risk study. Primary, secondary, and exploratory analyses will be tested in the framework of linear mixed effects to examine the comparative effectiveness of treatment on the change in pain severity, function (Aim 1) and QoL scores and opioid dose (Aim 2) over 12-months between the two groups. Tests will be performed at a two-tailed significance level of 0.025 for each co-primary outcome (Aim 1) and a 0.05 significance level for the secondary outcomes (Aim 2). Contrasts will be used to test for an overall treatment effect at 6 and 12 months. Detailed Statistical Analysis Plan is located in Appendix.

If and only if, the planned superiority analysis does not find statistically significant differences between the two groups, we will employ a formal non-inferiority analysis as a pre-specified secondary analysis. This analysis would employ mixed effects models to determine 95% confidence intervals for the difference between the mean scores of the primary outcomes of pain (BPI) and function (ODI) between the two groups, with the purpose of assessing whether MBT is non-inferior to CBT for treatment of people with opioid-treated chronic low back pain, using acceptable difference delta values of 0.8 for the BPI pain scale and 8.0 for the ODI function scale.

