6.2 Randomization and Blinding of Study Intervention

N/A Participants will be randomized equally between MM and CBT arms (1:1 ratio), using a permuted blocks of random size strategy, stratified by site and prepared by the study statistician. Sealed envelopes with group assignment will be distributed consecutively; participants will break the seal after completing the baseline assessments.

Although participants, therapists and outcome assessors cannot be blinded to the study intervention, investigators and analysts will be blinded to the group status until the first stages of analysis and reporting are completed.

7 Study Procedures

The initial eligibility screening will take place by phone or in person (see Section 5.4.2 for details). Those eligible and interested in participation will meet in person with the study coordinator.

In-Person Consent/Enrollment/Baseline/Randomization

During the in-person meeting at baseline, eligibility will be confirmed. Eligible, interested individuals will complete the written informed consent procedures and be assigned a study ID number (approximately 20 minutes to complete, on average). Then they will complete the baseline questionnaires (approximately 55 minutes to complete, on average), followed by a brief videorecorded activity focused on the assessment of physical function (approximately 10 minutes to complete). This videorecorded activity will involve the participant performing the standardized Timed Up and Go (TUG) test, evaluating a participant ability to stand up from a chair, walk 3 meters, before walking back to the chair and sitting down,^{110,111} and a brief interview about the impact of back pain and opioid therapy, and expectations/impact of the study. Then participants will be randomized (1:1 block scheme prepared by the study statistician) to the MM or CBT groups, and receive information about details and scheduling of their respective interventions. All baseline questionnaires can be completed verbally, electronically, or on paper if the participant requests it.

Virtual Consent/Enrollment/Baseline/Randomization

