8.1 Sample Size Determination

We conservatively estimate the need to screen approximately 4,000 individuals to enroll up to 800 participants. In our pilot RCT of MM for opioid-treated CLBP, 304 potential participants were identified through the EHR data and clinician and self-referrals; 87 were screened, 48 were eligible and 35 were enrolled.¹⁷ During the 26-week pilot study, no participant withdrew, and two (5.7%) missed the final assessment. In the PI’s other trial of MM, 92% of 123 alcohol dependent adults completed a 1-year follow-up.⁴⁷ Our other studies have also had excellent recruitment and retention. Two RCTs of MM led by [name] had an overall 95% (540/567) retention rate over a 9 month follow-up. For these studies, 2,080 adults were screened, 183 were found eligible but declined and 567 (27.3%) were enrolled.^{46,48}

Using estimates from systematic reviews and meta-analyses, comparing MM and CBT to a wait-list controls,^{10,18-20,35} and from two previous trials of MM in opioid-treated chronic pain,^{15,17} as outlined in the Background, we assume an effect size $d=0.25$ of MM vs CBT for pain severity and function, and a dropout rate of not more than 20%. We adjust for multiplicity of the co-primary outcomes by using a significance level of 0.025 for each Aim 1 outcome, for an overall significance level of at most 0.05. With 383 participants randomized to each of the treatment arms (766 total), a two-sample test with a significance level 0.025 and at most a 20% dropout rate is powered to detect an effect size of 0.25 of MM versus CBT for primary outcomes with power of 0.80.

To assess power to detect treatment differences between the proposed subgroups, we used the sample size of N=383 per group and a significance level $\alpha=0.05$ (i.e., not adjusting for multiplicity). Based on the existing literature and prior studies by Co-Investigators, we anticipate that approximately 35% of the study participants will show an elevated level of negative affect and approximately 45% of the sample will have an elevated level of opioid-related aberrant drug use

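### The fixed 0.025/0.025 split for pain and function is valid, but Holm's procedure gives more power under the same 0.05 familywise bound, with the same participants

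*Combined protocol and SAP*

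**What the plan says.** The sample size section (8.1) adjusts for two co-primary outcomes by "using a significance level of 0.025 for each Aim 1 outcome, for an overall significance level of at most 0.05". Section 8.2 repeats the rule for the analysis: "Tests will be performed at a two-tailed significance level of 0.025 for each co-primary outcome (Aim 1"). The non-inferiority paragraph of 8.2 identifies the pair as "the primary outcomes of pain (BPI) and function (ODI) between the two groups".

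The design figures are all in 8.1: "we assume an effect size $d=0.25$ of MM vs CBT for pain severity and function", "a dropout rate of not more than 20" percent, and "With 383 participants randomized to each of the treatment arms (766 total"), for a stated power of 0.80 per primary outcome.

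The supplied text contains no step-down or alpha-recycling rule, no power for showing both outcomes, and no correlation between them. Section 8.2 refers to a detailed SAP in an Appendix, which is not part of the supplied text.

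**The concern.** A fixed split never uses the alpha released when one hypothesis is rejected. If pain is significant at 0.025, the only null hypothesis still in play is the one for function. It can be tested at 0.05 and the familywise bound still holds. The plan tests it at 0.025.

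This matters because Hypothesis 1 (section 2.2) and the primary objective (section 3) claim a benefit on pain and on function together. The plan reports power for each outcome separately, and the chance of showing both is clearly lower than 0.80. The fixed rule also leaves almost no margin if dropout exceeds the planned 20%.

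**Working it through.** **Inputs from section 8.1:** d = 0.25 on both outcomes, 383 randomised per arm, 20% dropout, two-sided 0.025 per outcome.

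**Assumption:** the correlation ρ between the two test statistics is not given. I use 0 to 0.7 and show 0.9 as a check.

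**Step 1: reproduce the plan.** The normal-approximation sample size is 305 evaluable per arm, and 305 / 0.8 = 381.25, so 382 randomised against the stated 383. For power, the evaluable number is 383 × 0.8 = 306.4 per arm. The noncentrality is 0.25 × √(306.4 / 2) = 3.094 and the critical value is 2.2414. Power = Φ(3.094 − 2.2414) = 0.803, so the planned 0.80 is reproduced.

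**Step 2: the two rules.** The test statistics are taken as bivariate normal, each with mean 3.094, unit variance and correlation ρ.
- Fixed: reject each outcome when |Z| > 2.2414.
- Holm: reject the outcome with the larger |Z| when it exceeds 2.2414; if so, reject the other when |Z| > 1.960.

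**Step 3: power with d = 0.25 on both outcomes** (numerical integration, confirmed by simulation).

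| ρ | Per outcome, fixed | Per outcome, Holm | Both, fixed | Both, Holm | At least one, either rule |
|---|---|---|---|---|---|
| 0 | 0.803 | 0.858 | 0.645 | 0.755 | 0.961 |
| 0.5 | 0.803 | 0.848 | 0.692 | 0.782 | 0.915 |
| 0.7 | 0.803 | 0.844 | 0.717 | 0.798 | 0.889 |
| 0.9 | 0.803 | 0.835 | 0.754 | 0.818 | 0.853 |

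Over ρ = 0 to 0.7, the chance that exactly one outcome is significant falls from 0.172-0.316 to 0.092-0.206.

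**Step 4: unequal effects** (d = 0.25 on the first outcome, ρ = 0 to 0.7).
- Second outcome d = 0.20: its power rises from 0.593 to 0.674-0.676.
- Second outcome d = 0.15: its power rises from 0.350 to 0.438-0.451.
- Second outcome d = 0: power for the real effect moves only from 0.803 to at most 0.805.

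**Step 5: error rates.**
- Both nulls true: Holm rejects something exactly when the fixed rule does, so the familywise error is identical, 0.049 at ρ = 0 and 0.043 at ρ = 0.7.
- One null true, d = 0.25 on the other: the false-positive chance on the null outcome is 0.025 with the fixed rule and 0.040-0.045 with Holm, still within 0.05.

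**Step 6: attrition margin.** Solving for per-outcome power of 0.80 gives 304.1 evaluable per arm with the fixed rule and 265.7 (ρ = 0) to 275.3 (ρ = 0.7) with Holm.
- Tolerated dropout, 1 − n / 383: 20.6% fixed; 30.6% to 28.1% Holm.
- Randomised per arm at 20% dropout, n / 0.8 rounded up: 381 fixed; 333 to 345 Holm. (The 381 differs from 382 in step 1 only because the evaluable number is not rounded first.)

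**The case against.** The strongest reply is that nothing needs repair. The plan sets two targets, 0.80 per outcome and overall alpha of at most 0.05, and meets both. It sets no target for power on both outcomes. That is true, and it is why this is a recommended improvement and not an error.

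Several narrower points deserve an answer.

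- **Equal error only as a bound.** When exactly one null is true, Holm spends more of the 0.05 (0.040-0.045 against 0.025). This stands. The guarantee is the common 0.05 ceiling, not equal error in every scenario.
- **The gain needs effects on both outcomes.** This also stands. With one zero effect the gain in power is negligible, and the chance of at least one success never changes. But section 8.1 itself assumes d = 0.25 for both.
- **If success required both outcomes, each could be tested at 0.05 without adjustment.** Power for both would then be 0.760-0.807, slightly above Holm's 0.755-0.798. But section 8.1 adjusts for multiplicity, so the plan wants each outcome claimable on its own. Holm keeps that and loses almost nothing on the joint claim.
- **Retention may exceed 80%.** Section 8.1 cites 92% and 95% in related trials. At those rates (352.4 and 363.9 evaluable per arm) the fixed rule already gives 0.859-0.871 per outcome, so the attrition margin matters less. Holm still adds about 0.03-0.05 per outcome.
- **One test per outcome is presupposed.** Section 8.2 speaks of contrasts at 6 and 12 months. If these were four separate tests at 0.025, the familywise error could reach 4 × 0.025 = 0.10 (1 − 0.975⁴ = 0.096 if independent), and neither rule as described would cover that. The point is fair and belongs in the same edit.
- **The SAP Appendix could not be checked.** If it already specifies a step-down rule, only section 8.2 needs aligning.

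**Conclusion.** The point holds as an efficiency gain; the present rule is valid provided each outcome has one confirmatory test. Holm rejects whenever the fixed split does, and sometimes the second outcome as well, under the same 0.05 familywise bound at any correlation. At the planned d = 0.25, the chance of failing to show both benefits falls from 28-35% to 20-24%.

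The size rests on true effects of 0.25 on both outcomes, 20% dropout and an assumed correlation of 0 to 0.7. The direction is the same at 0.9 and with a smaller non-zero second effect. The arithmetic is secure. What the SAP Appendix says is unknown.

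**What to change.** In section 8.2, replace the fixed rule for Aim 1 with Holm's: test the smaller of the two p-values (BPI pain, ODI) at two-sided 0.025; if it is significant, test the other at two-sided 0.05; otherwise stop. Keep 383 per arm and the overall 0.05 statement in 8.1, which stays true. Make the SAP Appendix agree.

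Subject to what the Appendix already says, clarify in the same edit that:
- BPI interference is supportive;
- each outcome has one confirmatory 6/12-month contrast or one joint test;
- the non-inferiority trigger ("the planned superiority analysis does not find statistically significant differences between the two groups") applies either per outcome or only when neither outcome is significant.

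**Cost.** No extra participants or data, but an amendment with its approval. It must be fixed before unblinding. That is feasible: no interim analysis is planned, and section 6.2 says "investigators and analysts will be blinded to the group status until the first stages of analysis and reporting are completed".

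**Downsides to accept.**
- Intervals matching Holm are less simple. When the second p-value lies between 0.025 and 0.05, Holm rejects while the 97.5% interval includes zero.
- The false-positive chance on a truly null second outcome is higher, within 0.05, as shown above.
- If the non-inferiority trigger is per outcome, it fires less often at d = 0.25 (0.142-0.156 instead of 0.197). If it means neither outcome is significant, it is unchanged at 0.04-0.11.

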| Main Inclusion Criteria | Moderate to severe chronic low back pain treated with \geq 15 mg/day of morphine-equivalent opioid dose for \geq 3 months; age 21+ |
| Main Exclusion Criteria | Prior formal MM or CBT training; inability to safely or reliably participate; current pregnancy; pre-existing borderline personality, delusional or bipolar (manic) disorders ("active" in the prior 12 months). Competent adults, meeting eligibility criteria, will be able to participate regardless of gender, race, ethnicity, religion or socioeconomic status. Prisoners, pregnant women and mentally impaired persons will not be included. Children, per eligibility criteria, are not eligible. |
| Study Interventions | Two behavioral therapies: Mindfulness Meditation and Cognitive Behavioral Therapy, delivered in addition to "usual care" |
| Intervention Duration | Both MM and CBT interventions will consist of 8 weekly two-hour therapist-led group-therapy sessions (total 16 hours); in addition, participants will be asked to engage in home practice of either MM or CBT techniques for at least 30 minutes/day, 6 days/week during the 12-month study. |
| Statistical Methodology | Primary outcome analysis: Intention-to-treat analysis in the framework of linear mixed effects to examine the comparative effectiveness of treatment on the change in pain severity, function (Aim 1) and quality of life scores and opioid dose (Aim 2) over 12-months between the two groups. Qualitative analysis for qualitative data. |

Schematic of Study Design

Contents

| | |
|---|----|
| Study Summary | 10 |
| Schematic of Study Design | 11 |
| 1 Key Roles | 15 |
| 2 Background and Introduction | 18 |
| 2.1 Background and Rationale | 18 |
| 2.2 Hypotheses | 18 |
| 2.3 Study Interventions | 19 |
| 2.4 Summary of Relevant Clinical Data | 19 |
| 2.5 Potential Risks and Benefits to Participants | 21 |
| 2.5.1 Known Potential Risks | 21 |
| 2.5.2 Protection Against Risks | 21 |
| 2.5.3 Potential Benefits to Participants | 18 |
| 3 Study Objectives and Purpose | 23 |
| 4 Study Design and Endpoints | 23 |
| 4.1 General Design | 23 |
| 4.1.1 Primary Study Endpoints | 24 |
| 4.1.2 Secondary Study Endpoints | 24 |
| 5 Study Participants – Enrollment and Withdrawal | 24 |
| 5.1 Participant Population | 25 |
| 5.2 Inclusion Criteria | 25 |
| 5.3 Exclusion Criteria | 25 |
| 5.4 Participant Screening for Recruitment | 26 |
| 5.4.1 Participant Identification | 26 |
| 5.4.2 Recruitment and Retention Strategies | 26 |

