9.2.3 Data Collection Tools (see Appendix for all data collection tools)

Outcome measures will assess pain intensity, physical function, quality of life, opioid dose, depression, anxiety, opioid misuse, pain acceptance, pain catastrophizing, mindfulness level, sleep problems, neuropathic pain, change in pain and function, health care utilization, loss of productivity, PTSD, loneliness, feeling loved, sites of pain, NIH minimum data set, treatment expectations/satisfaction, non-protocol treatment, MM/CBT practice, adverse events, demographics, well-being, and experiences of those who reduced their opioid dose the most.

Primary Outcomes

Pain intensity will be assessed using the 0-10 point *Numerical Rating Scale* (NRS) from the Brief Pain Inventory (BPI).^{49,50} The NRS is reliable and valid in CLBP ($\alpha=0.85$).⁵³ A 1-point between-group difference is considered a minimal important change (MIC).^{28,29}

Physical function will be measured using the validated *Oswestry Disability Index* (ODI),^{51,52} which has good internal consistency (0.76-0.90), is reliable (0.83-0.99) and responsive to change.^{56,72} Its total score (0-100) reflects the percent of disability. A reduction of 4-10 points constitutes the MIC.²⁸⁻³⁰ In addition, functional status will also be assessed with 7 pain interference items from the BPI.^{49,50,53}

Secondary Outcomes

Quality of life (QoL) will be assessed using the validated *Medical Outcomes Study Short Form Health Survey* (SF-12 v.2),^{54,55} a common measure of health and QoL in CLBP.⁵⁶ The SF-12 has good reliability in CLBP ($\alpha=0.76-0.89$), and yields one composite and two component (mental and physical) scores measuring general health and QoL.^{54,55}

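### The fallback non-inferiority analysis in 8.2 names no analysis population and no attendance-based support, although non-attendance moves the comparison towards a non-inferiority finding

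*Combined protocol and SAP*

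**What the plan says.** Section 8.2 runs non-inferiority only when the superiority analysis finds no significant difference. In that case "we will employ a formal non-inferiority analysis as a pre-specified secondary analysis", using mixed models, 95% confidence intervals and margins of 0.8 on BPI pain and 8.0 on the ODI. It names no analysis population for this step. It points to a detailed SAP in an appendix, which is not part of the text reviewed here.

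The one population named anywhere is in the Study Summary: "Primary outcome analysis: Intention-to-treat analysis in the framework of linear mixed effects".

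Section 5.7.3 keeps collecting outcomes from people who stop attending sessions but do not withdraw. Section 9.2.3 records session attendance, home practice and non-protocol treatment. The protocol text does not use any of these to define an analysis set.

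Section 9.2.3 also gives the yardsticks. For pain, "A 1-point between-group difference is considered a minimal important change (MIC"). For the ODI, the minimal important change (MIC) is a reduction of 4 to 10 points.

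**The concern.** In a superiority test, keeping non-attenders in the comparison is conservative, because they dilute a real difference. In a non-inferiority test the same dilution helps the claim. If CBT works better than MM in people who attend, non-attendance in both arms shrinks the observed deficit of MM and makes a confidence limit inside the margin easier to obtain.

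Both arms are group courses of eight sessions, so attendance is the exposure. A non-inferiority statement would feed directly into the choice between MM and CBT that the trial is meant to inform. Without an attendance-based analysis, a null result cannot be separated into two therapies working equally well and two therapies that few people received.

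**Working it through.** **1. The plan's own sample size.** Inputs from 8.1 and 8.2: effect size 0.25, two-sided alpha 0.025, power 0.80, dropout at most 20%.

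- n per arm = 2(2.241 + 0.842)² / 0.25² = 304.2. The t distribution gives 305.4, rounded up to 306.
- 306 / 0.8 = 382.5, so 383. This agrees with "With 383 participants randomized to each of the treatment arms (766 total").

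I therefore use 306 completers per arm. The documents give no sample size or power for non-inferiority.

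**2. Dilution.** Let q be the share not attending, equal in both arms, with no arm difference among non-attenders. The intention-to-treat difference is then (1 − q) times the difference in attenders, and a margin M corresponds to M/(1 − q) in attenders. The documents give no value for q, so a range is shown.

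| q | Pain margin in attenders | ODI margin in attenders |
|---|---|---|
| 0% | 0.80 | 8.0 |
| 10% | 0.89 | 8.9 |
| 20% | 1.00 | 10.0 |
| 30% | 1.14 | 11.4 |
| 40% | 1.33 | 13.3 |

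The pain margin reaches the 1-point MIC at q = 20%. The ODI margin lies inside the 4-10 range even at full attendance; 20% takes it to the top of that range.

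**3. The superiority gate at the pilot SDs.** Section 2.4 gives baseline SDs of 1.4 (pain) and 11.4 (disability). I apply the gate to each outcome at two-sided 0.025 and treat the comparison as a two-sample difference.

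- SE = SD × √(2/306): 0.113 for pain and 0.922 for ODI.
- A result is non-significant when the absolute difference is below 2.241 × SE: 0.254 and 2.07.
- The 95% limit is then at most (2.241 + 1.960) × SE: 0.476 and 3.87. Both lie well inside 0.8 and 8.0.
- If attenders differ by the MIC (1.0 pain, 10 ODI), the chance of a non-significant result followed by a non-inferiority claim is about 0 at q = 20%. At q = 30% it is 0.00004 for pain and about 0 for ODI.
- The margins start to exclude some non-significant results only when the SD exceeds 0.8/(4.201 × √(2/306)) = 2.36 for pain, or 23.6 for ODI.

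**4. A larger SD.** Take pain SD 2.0 (assumed): SE = 0.1617 and the gate is at 0.362. The largest limit after a non-significant result is 0.679, still below 0.8, so the gate alone decides. With attenders truly 0.8 worse on MM, the false-claim rate is Φ(2.241 − 0.8(1 − q)/0.1617):

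| q | Intention-to-treat difference | False-claim rate |
|---|---|---|
| 0% | 0.80 | 0.003 |
| 20% | 0.64 | 0.043 |
| 30% | 0.56 | 0.111 |
| 40% | 0.48 | 0.23 |

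With attenders a full 1.0 point worse, the rates at 20%, 30% and 40% are 0.003, 0.018 and 0.07.

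**5. What a second analysis does** (SD 2.0, q = 30%, attenders 0.8 worse).

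- *Per-protocol set*, 306 × 0.7 = 214 per arm, limit also required below 0.8. By simulation, the false-claim rate falls from 11% to 2.2%. The chance of a claim when there is no difference falls from 97.5% to 96.6%. This assumes that the same kind of people attend in both arms.
- *Complier-average estimate*, the intention-to-treat difference divided by 0.7. The claim then needs a difference below 0.8 × 0.7 − 1.96 × 0.1617 = 0.243. The false-claim rate is Φ((0.243 − 0.56)/0.1617) = 2.5%. The chance of a claim at no difference is Φ(0.243/0.1617) − Φ(−2.241) = 0.934 − 0.0125 = 92.1%.

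**The case against.** The strongest objection is the gate. A true difference large enough to matter would usually be significant in favour of CBT, and the non-inferiority step would never be reached. At the pilot SDs this stands in full. A reader might infer that low attendance alone is likely to produce a false finding of non-inferiority, and on those SDs the documents do not support that. But the gate works only through the SE. The pilot SDs are baseline values from 35 people, and entry requires pain of at least 3 and ODI of at least 21, which truncates baseline spread. Follow-up spread could be larger; adjustment for baseline could make the effective SD smaller. The relevant SD is unknown.

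A reader might also take the 20% in 8.1 as the non-attendance rate. It is dropout. No attendance rate is given, and the plan works to keep attendance high: payment per session and an adherence bonus (5.4.2, 5.6.6), telephone follow-up of missed sessions (11.4) and regular check-ins (7.2.3). At 10% non-attendance the pain margin in attenders is 0.89, below the MIC.

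Finally, this is a pragmatic trial, and a set chosen after randomisation should not overrule a randomised comparison. That is fair. It argues for keeping intention-to-treat as the main analysis and for qualifying the wording when the two disagree. It does not argue for leaving attendance out.

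**Conclusion.** The gap is real, and its size is conditional. The protocol text names no population for non-inferiority, names only intention-to-treat elsewhere, and plans no supporting analysis by attendance. To say that the claim definitely rests on intention-to-treat alone would go too far, because the detailed SAP appendix was not available.

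Dilution favours the claim whenever CBT is truly better in attenders. Its size depends on two quantities that the documents do not give: the non-attendance rate and the follow-up SD. At the pilot SDs, the false-claim risk at an MIC-sized attender difference is close to zero for 20-30% non-attendance, but the margins then test nothing beyond non-significance. At an assumed pain SD of 2.0 with attenders 0.8 worse, the risk is about 4% at 20%, 11% at 30% and 23% at 40%, against a nominal one-sided 2.5%. All of this assumes equal non-attendance in both arms and no arm difference among non-attenders.

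A reader might infer that dilution is what makes both margins as large as the MIC. For pain this needs about 20% non-attendance. For the ODI, 8.0 is already inside the 4-10 range, which is worded as a reduction and not as a between-group difference.

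The change is worth making: it is cheap and uses data already planned.

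**What to change.** In 8.2 (and in the SAP appendix, if it is silent):

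- Name intention-to-treat as the main non-inferiority set.
- Add one attendance-based analysis from the researcher-recorded attendance. A complier-average estimate is preferable; a per-protocol set with a session threshold fixed before unblinding is the alternative.
- Report both with the margins of 0.8 and 8.0. Describe MM as non-inferior without qualification only if the two agree; otherwise report the intention-to-treat result with the disagreement stated.

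Cost: SAP wording and one more model, with no new data. In the example above (SD 2.0, 30% non-attendance), the chance of an unqualified claim when the arms are equal falls from 97.5% to 96.6% with the per-protocol set, or to 92.1% with the complier-average estimate. The per-protocol set is not fully protected by randomisation. The complier-average estimate relies on the assumption of no arm difference among non-attenders. Either should therefore support intention-to-treat and not replace it.
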